## 16. Results reporting.

---

The results obtained during the study protocol will be the sponsor's responsibility, who has the obligation to report the results to the competent authorities. Also, each one of the participating investigators will receive a report of the results.

In order to disseminate the obtained scientific knowledge, the publication of the study in an international magazine will be procured.

## 17. Identification, safety and therapeutic compliance procedures of the research subjects.

---

### *17.1 Recruitment*

Patients will be recruited at the ophthalmology practice of the participant Contract Research Organization and a goal of 20 scrutinized and randomized patients is contemplated.

### *17.2 Patient's identification*

All the participants of the study will be identified with a number and the initials of their name.

In the scrutiny stage, the participant number will be assigned consecutively, using 3 digits and in the enrollment stage a number will be assigned according to an electronic randomization system. Once the subject is included a patient number will be assigned and it will be composed of 3 molecule digits, 2 of the center number and 3 digits of the assigned consecutive number in the investigation center.

Example:

**080701001** (molecule number/center number/patient number in the center).

### *17.4 Patient elimination*

The causes for a withdrawal of the study from a patient might be the following:

Subject's decision. The patient who wishes to leave the study for any reason can do so at any time, but the investigator must be informed of this. In all cases, the investigator must try to get in contact with the patient as soon as possible for a final assessment in order to do the following:

Document the patient's decision in clinical notes,

Obtain the reason(s) of the departure and record them in the departure form of the CRF,

Assess the clinical state of the patient,

If necessary, take the appropriate therapeutic measures: management of an adverse event or concomitant disease.

Investigator's decision: Especially if there is an adverse event and if the investigator considers that this might threaten the patient's health, actions will be taken as described on the adverse events section or if there is an important disease that needs the prescription of a drug incompatible with the purpose of the study. It will be reported in clinical notes and a serious adverse events report format will be filled and the Research Ethics Committee, the clinical monitor and Pharmacovigilance of Laboratorios Sophia will be informed of this.

A wrongful inclusion according to the protocol. The decision to keep the patient in the will be taken conjointly by the investigator and the sponsor.

Other reasons (insufficient response, need for another treatment).

In all cases, the available data will be kept for safety analysis (assessable population for intention to treat).

### *17.5 Investigational products recall*

In case of an investigational product recall (decided by the competent authorities or by the sponsor), the sponsor will inform the principal investigator immediately.

The investigator, along with the sponsor's representatives (clinical monitor) must urgently do the following:

- ❖ Stop the patient's supply of the affected investigational products.
- ❖ Inform the involved patients to immediately suspend the administration of those investigational products and take them to the center.

- ❖ The monitor will organize the return to proceed to destroy the study medication, both the used and the non-used ones for Laboratorios Sophia, as per their procedures.

### *17.6 Treatment compliance*

The study drug administration compliance from the patients will be assessed in the Laboratorios Sophia facilities once the dropper bottles of each patient are returned by the investigator; each bottle will be weighed in an analytical balance and the difference will be obtained regarding the initial weight of the container, all values over 80% will be considered as appropriate compliance to the treatment.

In case the study drug compliance is less than 80%, the obtained results will be considered to be analyzed via the intention to treat, see statistical analysis section.

## **18. ADVERSE EVENTS.**

---

### *18.1 Adverse event, definition and communication*

#### *18.1.1 General aspects*

During the study, adverse events (AE) may occur, these can be associated or not with the study drug.

If at any moment any of the study patients would have any adverse event classified as serious deriving from the administration of the drug, actions will be taken as per the guidelines of Official Mexican Standard 220 SSA1 2012 Installation and operation of Pharmacovigilance. The administration of the drug will be interrupted and the administration of an alternative therapy will be ordered, at the discretion of the principal investigator.

An adverse event is any adverse medical occurrence in a clinical research patient or subject to whom a pharmaceutical product has been administered and that does not necessarily have a causal relationship with this treatment. Therefore, an AE might be any unfavorable and non-intentional sign (including an abnormal laboratory finding), symptom or disease temporarily associated with the use of a (investigational) drug product whether it is related or not.

The investigator must report the adverse events occurred during the realization of the study from the moment a patient signs the informed consent to be included in the clinical study until the last procedure described in the approved study protocol version has ended.

In all cases, the etiology must be identified as far as possible and notify the study sponsor. An “unexpected adverse event” is any AE that is not identified in nature, seriousness or frequency in the investigator’s brochure or in the risks information described in this protocol.

## *18.2 Classification and severity*

### *18.2.1 Classification*

Adverse events, according to their importance, are divided in two categories: “serious” and “non-serious”.

This classification determines the procedure to be used to report or document the adverse event.

A **serious adverse event** is that which:

- ❖ Endangers or causes the patient’s death.
- ❖ Makes it necessary to be hospitalized or extend the hospital stay.
- ❖ It is a motive for persistent or significant disability.
- ❖ It is a motive for alterations or malformations in the newborn.

A non-serious adverse event is that which does not fulfill the aforementioned criteria.

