### 12.2.3 Elimination criteria for the subject included on the study

1. Signs and symptoms evolving to serious tear film dysfunction syndrome detected on any treatment visit.
  - a. TBUT < 5 seconds
  - b. Peripheral or secondary leucoma to corneal scarring
  - c. Phlycten
  - d. Corneal keratinization
  - e. Epithelial squamous metaplasia
  - f. Corneal conjunctivalization
  - g. Corneal neovascularization
  - h. Corneal ulcers
  - i. Any secondary injury permanently reducing the visual acuity, as a consequence of the tear film dysfunction.
2. Added ocular surface diseases requiring a different treatment to PRO-087 or added treatments indicated for a new diagnose.
3. Opacities on ocular clear media (cornea, lens, vitreous body) avoiding to assess the anterior chamber or the posterior segment.
4. Decision of the subject
5. Difficulty to attend the follow-up appointments.
6. Added or self-prescribed non-authorized treatments
7. Herbal treatments affecting the course of the disease or producing other complications not related with the disease
8. Systemic diseases requiring an immunomodulator, immunosuppressing or biological treatments affecting any inflammatory cascade line.

9. Retinal diseases secondary to chronic-degenerating diseases requiring treatment to preserve the function and/or anatomy
10. Inflammatory retinal diseases
11. Uveitis presentation installation at any ocular uveal level
12. Clinical picture meaning an ophthalmic urgency requiring immediate treatment
13. Ocular diseases requiring surgical treatment
14. Ocular diseases requiring intraocular injections

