#### 14.3.1 Safety Parameters

Parameters	Value
Best-corrected visual acuity	No change of 1 line in the Snellen chart or 1 logarithmic point (logMAR)
Intraocular pressure	Measurements below 7 mmHg and over 21 mmHg
Corneal depithelization	Percentage of the damaged epithelium of the ocular surface, reduction of staining according to the Oxford scale.
Anterior segment examination	Abnormalities on any of the comprised structures: Cornea, iris, pupil, iris-corneal angle and crystalline.
Posterior segment examination	Abnormalities on any of the comprised structures: Vitreous, retina, macula and optic nerve.
Tear film break-up time	Reduction of more than 20% over the baseline time.
Schirmer test	Reduction of more than 20%
Adverse events	Presence of adverse events modifying some of the abovementioned criteria or others evaluated as serious.
OSDI	Increase of the score of more than 10 points.

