### *18.2.2 Adverse events severity*

The severity degree of the adverse events must be assessed by the investigator in charge or the person in charge of that function, as per the intensity of the clinical manifestations.

- ❖ **Mild severity** is considered for those adverse events that do NOT interfere with everyday activities, they may or may not require the drug suspension.
- ❖ **Moderate severity** is considered for those adverse events that interfere with everyday activities (they might cause work or school absence) without directly threatening the patient's life, they may or may not require the drug suspension.
- ❖ **Serious severity** is considered for those adverse events that prevent someone from doing everyday activities.

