#### *18.5.6 Reporting of serious adverse events*

An active search of SAEs must be carried out using the spontaneous reports from the patient, the physical examinations and the interviews carried out by the investigator during the various visits.

If the AE leads to the interruption of the trial, the investigator must complete the CRF, in the corresponding section to the termination of the trial and specify if the event is serious or not.

A serious adverse events form must be filled by the principal investigator or the doctor in charge and it must be sent to the sponsor within 24 hours of the notification; even if all the information required is not available at that moment. All the subsequently gathered information must be sent immediately once it is available. The investigator must monitor the SAE properly and in its entirety. In any moment an updated report of the SAE must be given and a written report must be elaborate when the SAE reaches a final result.

Also, the Research Ethics Committees must be informed of the SAEs as well as the regulating authorities.

There must be a notification on all the SAEs as soon as they become known, according to the aforementioned definitions and regardless of the treatment or relationship to the drug being investigated.

The investigator must notify the sponsor about the event sending said notification within 24 hours after the event has become known, the “Serious Adverse Event Report” form (“first notification”) must be sent via **e-mail** with all the available information on the serious adverse event to the Pharmacovigilance Department of Laboratorios Sophia, S.A. de C.V. and attach a copy of the e-mail to the monitoring person in charge of the center.

Person in charge of Pharmacovigilance:

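### The serious-event definition in 18.2.1 has no medically important or sight-threatening criterion, so outpatient ocular emergencies are not assured 24-hour reporting; separately, the word serious carries two meanings

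*Combined protocol and SAP*

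**What the plan says.** Section 18.2.1 splits adverse events into serious and non-serious and lets that class decide how each is reported. An event is serious if one of four things is true: "Endangers or causes the patient’s death"; it leads to a hospital admission or prolongs one; "It is a motive for persistent or significant disability"; or it causes an abnormality in a newborn. The section then adds: "A non-serious adverse event is that which does not fulfill the aforementioned criteria".

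Section 18.5.6 requires the investigator to notify the sponsor of a serious event "within 24 hours after the event has become known", and ties this to the definitions given before it. Section 18.3 sends non-serious events to the case report form.

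Section 12.2.3 lists events that end participation. They include corneal ulcers (item 1h), uveitis (item 11) and item 12: "Clinical picture meaning an ophthalmic urgency requiring immediate treatment".

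Section 17.4 says that when the investigator withdraws a patient, especially for an adverse event that may threaten health, a serious-event form is completed and the ethics committee, the monitor and pharmacovigilance are told.

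Section 18.2.2 grades severity as mild, moderate or serious, the last being "for those adverse events that prevent someone from doing everyday activities". The adverse-event row of table 14.3.1 reads: "Presence of adverse events modifying some of the abovementioned criteria or others evaluated as serious". Table 14.1.2 has a nearly identical row.

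**The concern.** The study drug is an eye drop, so the worst foreseeable treatment-related harms are local: ulceration, intraocular inflammation, acute threats to sight. Such events are often managed without admission and can resolve without lasting damage. A definition built only on death, hospital stay, disability and newborn harm can miss them while they are active, which is when quick notice to the sponsor matters most.

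The second matter is one of counting. If serious means both a regulatory class and a severity grade, two people filling in the safety table from the same records can count different subjects.

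**Working it through.** The main point is a reading of provisions against each other. The only arithmetic is in steps 2 and 4.

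**Step 1. Test the named events against the four criteria.** Take a corneal ulcer, uveitis or ophthalmic urgency, and assume outpatient care, no danger to life, and no lasting or significant disability.

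- Death or danger of death: not met.
- Hospital admission or longer stay: not met.
- Disability: not met under the assumption. The criterion is worded as either/or, so a temporary but significant loss of vision could meet it.
- Newborn abnormality: not applicable.

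The result is 0 of 4, and the closing sentence makes the event non-serious. No other section adds a further category.

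**Step 2. See what the class controls.**

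| Provision | Serious event | Non-serious event |
|---|---|---|
| Reporting (18.5.6, 18.3, 19) | Form to the sponsor in 24 hours | Case report form, checked at monitoring visits; electronic entry within 72 hours of the visit |
| Treatment code (7.3) | May be consulted with sponsor authorisation | No provision |
| Actions in 18.1.1 | Triggered if due to the drug | Not triggered |
| After the trial (18.6.1) | Notified if within 15 days | Notified only if the investigator thinks it may be related |

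For an event found at a visit, the difference between the two limits is 72 − 24 = 48 hours. For an event learned of between visits, the 72-hour limit gives no protection, because it runs from a visit date. The last three treatment-period visits are on days 30, 60 and 90, which is 30 days apart. Section 18.1.1 also asks that the sponsor be notified in all cases, but gives no time.

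**Step 3. Test whether 17.4 fills the gap.**

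- The form is required under the heading of investigator decision. The text does not say whether elimination under 12.2.3 counts as such a decision.
- The trigger is a judgement that health may be threatened, or an important disease needing an incompatible drug.
- Need for another treatment also appears under a separate heading of other reasons, with no form attached. An ulcer or uveitis could be filed there.
- No deadline is given. One can argue that the 24 hours in 18.5.6 attach to the form itself, but 18.5.6 also ties notification to the 18.2.1 definitions.
- The event is not reclassified, so 7.3, 18.1.1 and the 15-day rule in 18.6.1 are unaffected.
- A serious-event form is asked for on an event that 18.2.1 calls non-serious. The two sections conflict.

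**Step 4. Test the second meaning of serious.** An event that stops daily activities but meets no 18.2.1 criterion is serious by grade and non-serious by class. If it alters no other row of table 14.3.1, whether it counts depends on the meaning chosen. The rule that uses this table allows changes in no more than 5% of subjects. I assume that it is applied row by row to the PRO-087 group. Section 13.3 plans 80 subjects, raised to 96 for losses:

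- With 80: 4/80 = 5.0%, within the limit; 5/80 = 6.25%, above it.
- With 96: 4/96 = 4.2%, within; 5/96 = 5.2%, above.

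Either way the fifth subject crosses the limit, so near the boundary one reclassified subject can change the conclusion.

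**The case against.** The strongest answer is section 17.4. All three named events are elimination criteria, so they would normally lead to withdrawal. In many cases the form would then be completed and the ethics committee, the monitor and pharmacovigilance told. This stands as a partial safeguard. A reader might infer from 18.2.1 alone that these events escape 24-hour reporting altogether; the documents do not support that. What they support is that such reporting is not assured, for the reasons in step 3.

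A reader might also infer that only permanent visual loss meets the disability criterion. It does not say so: significant disability is enough, and the gap is limited to events that cause neither kind.

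Third, the safety table does not depend on the seriousness label to pick up these harms. Table 14.3.1 has separate rows for corneal and anterior-segment abnormalities, and its adverse-event row also takes in events that alter another row. This stands. The gap concerns prompt notice and code access rather than whether such findings are tabulated.

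On terminology, the double use of serious is probably a matter of translation: the text also uses it as the top grade for Schirmer results, hyperemia and photophobia. That makes the remedy easy, but the two tables remain ambiguous. A reader might go further and say that a trivial event would be counted as serious. That is not supported, because the grade requires that daily activities be prevented.

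**Conclusion.** The point holds in this form. The serious-event definition is a closed list of four with no medically important or sight-threatening criterion. At least three event types that the protocol itself foresees fall outside it when managed without admission and without lasting or significant disability. Four procedures depend on the class: code access (7.3), the actions in 18.1.1, 24-hour reporting (18.5.6) and post-trial notification (18.6.1). The only backstop for prompt notice is 17.4, which is discretionary, undated and at odds with 18.2.1.

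The terminology problem is separate and smaller. It affects only events that alter no other row of the tables.

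The documents give no expected frequency for these events, so the number of late reports cannot be estimated. The national pharmacovigilance standard is cited only for actions once an event is serious, and its content is not in the documents, so nothing here rests on it. This should be corrected because it bears on safety oversight and costs little. It does not threaten the efficacy analysis.

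**What to change.** 1. In 18.2.1, add a criterion for medically important events, including any that threaten sight, with 12.2.3 items 1h, 11 and 12 as examples.
2. In 18.2.2, rename the top severity grade *severe*.
3. In the adverse-event rows of tables 14.1.2 and 14.3.1, write *serious as defined in 18.2.1*.
4. Reconcile 17.4, 18.2.1 and 18.5.6 so that the same events trigger the serious-event form and the 24-hour clock, and state whether elimination under 12.2.3 triggers both.
5. A wider definition also widens what sets off the actions in 18.1.1. The sponsor must reconcile that section with the new wording; no treatment rule is proposed here.

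The cost is a change of wording in the protocol and report forms, and a few more expedited reports. Sample size, visits and the planned tests are unchanged.

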### *18.2.2 Adverse events severity*

The severity degree of the adverse events must be assessed by the investigator in charge or the person in charge of that function, as per the intensity of the clinical manifestations.

- ❖ **Mild severity** is considered for those adverse events that do NOT interfere with everyday activities, they may or may not require the drug suspension.
- ❖ **Moderate severity** is considered for those adverse events that interfere with everyday activities (they might cause work or school absence) without directly threatening the patient's life, they may or may not require the drug suspension.
- ❖ **Serious severity** is considered for those adverse events that prevent someone from doing everyday activities.

### *18.3 Non-serious adverse events report*

Reports of adverse events classified as “non-serious” must be made in the specific section of the case report form specific of the clinical protocol, as per the statements in the case report form completion guide.

During each monitoring visit the right completion of the non-serious adverse event report will be verified in the specific section of the case report form. It must be ensured that, before the base closure of the study, the non-serious adverse events are completed with the adverse events final resolution and the entirety of the requested information in the case report form.

#### *18.4 Adverse events report characteristics*

The investigator in charge and/or the person in charge of said function must report all serious or non-serious adverse events occurring during the study development, granting a diagnosis (name) to the condition(s) seen in the patient.

It must be ensured that the adverse events are reported correctly grouping the signs and symptoms of the patient in clinical diagnosis.

In those cases where the presence of various adverse events is detected at once and that there is evidence of none of them corresponding to the same pathological entity, each one of the adverse events must be reported separately.

For the scheduled surgical interventions a clinical diagnosis that was the cause to do the surgery must be reported and not the surgical event itself. For example: cholecystectomy (surgical event-NOT reported as an adverse event), acute cholecystitis (clinical diagnosis-reported as an adverse event).

The adverse events reports must state the date/time of start, date/hour of termination, evolution and actions taken according to the following:

- ❖ Resolved.
- ❖ Resolved with sequelae.
- ❖ Being resolved.
- ❖ Not resolved.
- ❖ Unknown.

Information on adverse events must be updated, stating the date of the type of final resolution of the adverse event or record them as “being solved” for those cases when the adverse event is still active.

### **18.5 Causality**

Based on the physical examination, signs and symptoms mentioned by the study subject, the principal investigator must state, on clinical judgement, if there is or not a causal relationship between the study drug(s) and the adverse event seen in the patient.

The way to classify the causal relationship with the study drug will be the following:

**18.5.1 Definitively related:** There is certainty that the adverse event is related to the investigational product.

**18.5.2 Probably related:** There is a strong likelihood that the adverse event is related to the investigational product.

**18.5.3 Possibly related:** There is a possibility of the investigational product being the cause of the adverse event, but other causes cannot be discarded.

**18.5.4 Not related:** There is evidence suggesting the adverse event is related to a cause different to the investigational product.

**18.5.5 Unknown:** Adverse events for which causality evaluations cannot be made.

Relationship between the study drug with the adverse events is established according to the following criteria:

- ❖ Previous experience with the drug.
- ❖ Knowledge of the adverse reactions with its use.
- ❖ Explanations for adverse reactions.

- ❖ Use of other drugs, concomitant diseases, non-pharmacological therapies, diagnostic tests or other procedures or, in its case, confounding factors.
- ❖ Time elapsed between the drug administration and the adverse event.
- ❖ Drug concentrations.
- ❖ Effects with re-exposure to the drug.

